9.4.5.2 Central Laboratory Assessments (On Treatment)

The following laboratory tests will be performed and submitted to the Central Laboratory for analysis as per the Study Assessment and Procedures in [Section 2](#). The following samples should be collected predose: Hematology, Chemistry, and Urinalysis.

Hematology	
Hemoglobin	
Hematocrit	
Total leukocyte count, including differential	
Platelet count	
Chemistry	
Aspartate aminotransferase (AST)	Total Protein
Alanine aminotransferase (ALT)	Albumin
Total bilirubin	Sodium
Direct bilirubin	Potassium
Alkaline phosphatase	Chloride
Lactate dehydrogenase (LDH)	Calcium

Creatinine Blood Urea Nitrogen (BUN) or Serum Urea Uric acid Fasting glucose	Phosphorus Magnesium Creatine kinase [REDACTED]
Urinalysis	
Protein	
Glucose	
Blood	
Leukocyte esterase	
Specific gravity	
pH	
Microscopic examination of the sediment if blood, protein or leukocytes esterase are positive on the dipstick	
[REDACTED]	

Abbreviations: ALT = alanine aminotransferase; AST = aspartate aminotransferase; BUN = blood urea nitrogen; CKD-EPI = Chronic Kidney Disease Epidemiology Collaboration; [REDACTED]
LDH = lactate dehydrogenase.

The Central Laboratory and designated reference laboratories for this study will perform the analysis of all scheduled laboratory tests and will provide reference ranges for these tests.

The detailed methods for specimen collection, handling, processing, shipping, and storage will be supplied in the Investigator’s Laboratory Manual provided by the Central Laboratory.

9.4.6 Imaging Safety Assessment

Not applicable.

9.5 Pharmacokinetics

Pharmacokinetics of BMS-986259 will be derived from serum concentration versus time. The PK parameters to be assessed include:

C _{max}	Maximum observed plasma concentration
T _{max}	Time of maximum observed plasma concentration
AUC(0-T)	Area under the plasma concentration-time curve from time zero to time of last quantifiable concentration
AUC(TAU)	Area under the concentration-time curve in one dosing interval
C _{trough}	Trough observed plasma concentration

Individual participant PK parameter values will be derived by non-compartmental methods by a validated PK analysis program. Actual times will be used for the analyses. When multiple procedures are required at a time point, prioritize that the PK samples are collected as close to the scheduled time point as possible.

Table 9.5-1: Pharmacokinetic [REDACTED] Sampling Schedule for All Participants (CV019010)

Study Day of Sample Collection	Event	Time ^a (Relative to BMS-986259 or Placebo Dose) Hour: Min	BMS-986259/ Placebo PK Serum Sample
Day 1	predose ^b	00:00	X
		3:00	X
		6:00	X
		8:00	X
		10:00	X
		14:00	X
Day 2	predose ^b	00:00	X
Day 3	predose ^b	00:00	X
Day 5	predose ^b	00:00	X
		3:00	X
		6:00	X
		8:00	X
		10:00	X
		14:00	X
Day 6	predose ^b	00:00	X
Day 8	predose ^b	00:00	X

Table 9.5-1: Pharmacokinetic [REDACTED] Sampling Schedule for All Participants (CV019010)

Study Day of Sample Collection	Event	Time ^a (Relative to BMS-986259 or Placebo Dose) Hour: Min	BMS-986259/ Placebo PK Serum Sample
Day 14 End of Study Visit ^c	predose ^b	00:00	X
Day 30 Follow-up [■]	Follow-up		

Abbreviations: [REDACTED] Min = minutes; [REDACTED] PK = pharmacokinetic.

- ^a All the PK samples should be collected as close to the scheduled time point as clinically feasible.
- ^b All predose samples should be taken (preferably with 30 minutes) prior to the start of subcutaneous injection. If it is known that a dose is going to be delayed, then the predose sample should be collected just prior to the delayed dose. However, if a predose sample is collected but the dose is delayed, an additional predose sample should not be collected.
- ^c If the study is ended early and the End of Study Visit takes place on Day 13 instead of Day 14, indicated Day 14 samples should be collected on Day 13.

[figure not shown]
The serum will be analyzed for BMS-986259 by a validated or a qualified enzyme-linked immunosorbent assay (ELISA) method assay. PK samples collected from a participant who received placebo will not be analyzed.

[figure not shown]

[figure not shown]
Detailed instructions for the PK blood collection, labeling, processing, storage, and shipping will be provided to the investigative site and home healthcare provider in the laboratory manual.

[figure not shown]
9.6 Pharmacodynamics

[figure not shown]
Pharmacodynamic parameters are not evaluated in this study.

[figure not shown]

9.9 Health Economics OR Medical Resource Utilization and Health Economics

Health Economics/Medical Resource Utilization and Health Economics parameters will not be evaluated in this study.

10 STATISTICAL CONSIDERATIONS

10.1 Sample Size Determination

The primary objective of the study is to evaluate safety and tolerability of BMS-986259. It is estimated there may be ~10% to 20% early treatment withdrawal. Approximately 72 participants will be randomized with 1:1 ratio to BMS-986259 subcutaneous QD and Placebo to have at least 60 completers by the end of the study. An estimation approach will be used for comparison between BMS-986259 and placebo for hypotension rate. Point estimates and associated 95% confidence intervals for event rate and relative risk ratio will be constructed to provide plausible range of values for the true comparison of interest.

The incidence of clinically relevant hypotension in the placebo group is estimated to be between ~ 5% to 15%. With N=60 and 1:1 treatment assignment ratio, the study will be able to detect a significant increase of clinical hypotension event compared to placebo ranging from 2.7 fold increase (eg, placebo rate =15%) to 5 fold increase (eg, placebo rate =5%).

10.2 Populations for Analyses

For purposes of analysis, the following populations are defined:

Population	Description
Enrolled	All participants who sign informed consent
Randomized	All participants who have been randomized by IRT system Randomized population will be used for Disposition, Demographic and baseline characteristic Analyses
Safety	All randomized participants who take at least 1 dose of double blind- study treatment. Participants will be included in the treatment group they were randomized to. eg, “Data in this data set will be analyzed based on randomized treatment, except in the following cases: 
 • If a participant received the same incorrect treatment throughout the study, then the participant will be analyzed based on the treatment received. • If a participant received study drug from more than one treatment group, and none of the administrations were consistent with the assigned randomized treatment group, then the participant will be analyzed based on the first treatment received. Safety Population will be used for all efficacy, safety ██████████ analyses
PK Population	All participants who have received at least one dose of treatment and have at least one valid PK measurement. If feasible, PK population will be used for all PK analyses

[figure not shown]
Abbreviations: IRT = Interactive Response Technology; PK = pharmacokinetic.

10.3 Statistical Analyses

A description of the participant population will be included in a statistical output report, including subgroups of age, gender and race.

10.3.1 Efficacy Analyses

Endpoint	Statistical Analysis Methods
Primary Not Applicable	
Secondary Not Applicable	

[figure not shown]

10.3.2 Safety Analyses

All safety analyses will be performed on the Safety Population.

Endpoint	Statistical Analysis Methods
Primary 
 ➤ Clinically relevant hypotension ➤ AEs ➤ Vital Signs ➤ Laboratory Test Results ➤ ECGs ➤ Physical Examination 	
The incidence of clinically relevant hypotension will be summarized by treatment. Point estimates and 95% CIs for event rates will be presented by treatment, together with point estimates and 95% CIs for the risk difference and relative risk between relaxin and placebo.
 
All recorded AEs will be listed and tabulated by system organ class, preferred term and treatment. Vital signs and clinical laboratory test results will be listed and summarized by treatment. Any significant physical examination findings, and clinical laboratory results will be listed. ECG readings will be evaluated by the investigator and abnormalities, if present, will be listed.

[figure not shown]

Abbreviations: [redacted] AE = adverse event; CI = confidence interval; ECG = electrocardiogram [redacted]

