Table 2-2: On-Treatment and Follow-up Procedural Outline (CV019010)

Procedure	Randomization D1 ^a	D 2	D 3	D 4	D 5	D 6	D 7 ^b	D 8 Visit ^c	D 9 ^b	D 10	D 11 ^b	D 12	D 13 ^d	D14 End of Study Visit c,d,e	D30 (± 2 days) Follow -Up Visit ^c	Notes
Assessment of Sign and Symptoms (NYHA class)	X					X ^f								X	X	
12-Lead ECG	X							X						X		ECGs should be recorded after the participant has been supine for at least 5 minutes. On Day 1, ECG will be collected pre-dose and at hours 2, 4, and 8. On Day 8 and Day 14, it will only be collected pre-dose.
Concomitant Medication Use	X	X	X	X	X	X	X	X	X	X	X	X	X	X	X	
Central Laboratory Assessments																

Table 2-2: On-Treatment and Follow-up Procedural Outline (CV019010)

Procedure	Randomization D1 ^a	D 2	D 3	D 4	D 5	D 6	D 7 ^b	D 8 Visit ^c	D 9 ^b	D 10	D 11 ^b	D 12	D 13 ^d	D14 End of Study Visit c,d,e	D30 (± 2 days) Follow -Up Visit ^c	Notes
Hematology and Serum Chemistry ^h	X	X	X			X ^f		X						X	X	See Section 9.4.5 .
Urinalysis ^h	X	X	X			X ^f		X						X	X	See Section 9.4.5.

[figure not shown]

Table 2-2: On-Treatment and Follow-up Procedural Outline (CV019010)

Procedure	Randomization D1 ^a	D 2	D 3	D 4	D 5	D 6	D 7 ^b	D 8 Visit ^c	D 9 ^b	D 10	D 11 ^b	D 12	D 13 ^d	D14 End of Study Visit c,d,e	D30 (± 2 days) Follow -Up Visit ^c	Notes
Adverse Event Reporting																
Monitor for Non-Serious Adverse Events & Serious Adverse Events	X	X	X	X	X	X	X	X	X	X	X	X	X	X	X	
Pharmacokinetic (PK) Assessments																
Blood PK Sampling	See Table 9.5-1 for sampling schedule														See Section 9.5 .	

Table 2-2: On-Treatment and Follow-up Procedural Outline (CV019010)

Procedure	Randomization D1 ^a	D 2	D 3	D 4	D 5	D 6	D 7 ^b	D 8 Visit ^c	D 9 ^b	D 10	D 11 ^b	D 12	D 13 ^d	D14 End of Study Visit c,d,e	D30 (± 2 days) Follow -Up Visit ^c	Notes
Clinical Drug Supplies																
Randomize	X															
Study Drug Administration	X	X	X	X	X	X	X	X	X	X	X	X	X	X		IP is administered subcutaneously once daily.

Abbreviations: [redacted] BP = blood pressure; COVID-19 = coronavirus disease 2019; D = Day; [redacted] ECG = electrocardiogram; HF = heart failure; ICF = informed consent form; IMP = investigational medicinal product;

IP = investigational product; IV = intravenous; [REDACTED] NYHA = New York Heart Association; PE = physical examination; PK = pharmacokinetic [REDACTED].

- a If screening and randomization are on the same day all evaluations can be performed only once.

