6.2 Exclusion Criteria

1) Target disease exceptions

- a) At randomization systolic blood pressure < 100 mmHg or > 145 mmHg.
- b) At randomization HR > 120 bpm.
- c) Acute cardiovascular condition other than HF decompensation either contributing to hospitalization or making participant unstable, such as acute MI/acute coronary syndrome, myocarditis, or arrhythmia with the exception of atrial fibrillation if HR within criteria limit.
- d) Cardiogenic shock (defined as SBP below 90 mmHg, signs of end-organ hypoperfusion plus need for intubation, mechanical circulatory support and other life-sustaining emergency measures) at presentation to ER or at any time before randomization.
- e) History of heart or any other solid organ transplant or currently on the transplant list.
- f) Recipient of ventricular assist devices.
- g) Use of any cardiac extracorporeal devices, within 12 weeks of study randomization. Cardiac Resynchronization Therapy Defibrillator (CRTD) and pacemakers/Implantable Cardioverter-Defibrillator (ICDs) are allowed, if implanted at least 4 weeks before randomization and no discharge within 4 weeks prior to randomization.
- h) Participants with contraindications to vasodilator therapy such as restrictive or obstructive cardiomyopathy, severe mitral or aortic stenosis.

2) Medical History and Concurrent Diseases

- a) Women cannot be pregnant or breastfeeding.
- b) Any major surgery within 12 weeks of study randomization.
- c) Suspected acute pulmonary disease such as pneumonia, exacerbation of asthma or COPD or severe chronic, pulmonary disease (eg, severe COPD, pulmonary fibrosis, patients with hypercapnia or requiring home oxygen or chronic systemic steroids)
- d) Hereditary or idiopathic pulmonary hypertension.
- e) History of stroke, or transient ischemic attack (TIA) within the 30 days prior to screening (according to the participants' records) or during screening.
- f) Acute coronary event within 30 days prior to screening or during screening (myocardial infarction, acute coronary syndrome, or unstable angina; according to the participants' records).

- g) Terminal non-cardiovascular disease such as cancer with life expectancy < 6 months.
- h) Severe liver disease such as cirrhosis with evidence of portal hypertension, or acute viral hepatitis.
- i) Participant is on dialysis or history of chronic or intermittent dialysis or ultrafiltration.

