9.4.3 Electrocardiograms

Planned time points for ECGs are listed in the Schedule of Activities (Section 2). Single standard 12-lead ECGs will be recorded after the participant has been resting for at least 5 minutes in the supine position.

The Investigator should review and assess all ECGs for any clinically significant abnormalities, and initial and date the report.

The site should follow their standard practices for performing ECGs. Below is guidance to be used as a reference, if needed:

In preparation for the ECG, ensure there is minimal interference between the skin surface and the electrode. Use alcohol to prepare the skin at each electrode site. Thick chest hair should be shaved to ensure sufficient contact.

[figure not shown]
Before attaching electrodes to pick-up points, spread the electrode with electrode gel. Place the electrodes on bony areas, avoiding large muscle masses, to achieve better tracings as described below. The participant must be supine and should refrain from movement during the ECG recording.

Ensure that the participant and the electrodes (including the neutral electrode) are not exposed to conducting objects, even if grounded.

- RL: On the right leg (inside calf, midway between knee and ankle)
- LL: On the left leg (inside calf, midway between knee and ankle)
- RA: Right arm (on the inside)
- LA: Left arm (on the inside)
- V1: 4th intercostal space, at right sternal margin
- V2: 4th intercostal space, at left sternal margin

- V3: Midway between V2 and V4
- V4: 5th intercostal space at left midclavicular line
- V5: Same transverse level at V4, at anterior axillary line
- V6: Same transverse level at V4, at left midaxillary line

Keep one original ECG (print-out or electronic copy) in the medical chart and ensure a copy, assessed, initialed and dated by the Investigator, is maintained in the source documents for the study.

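### Section 10.3.2 lists abnormal ECG readings without a summary by treatment or against baseline, unlike vital signs and laboratory results in the same cell

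*Combined protocol and SAP*

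**What the plan says.** Section 10.3.2 groups several safety measures in one row headed Primary. After clinically relevant hypotension, AEs and vital signs, the row continues "Laboratory Test Results ➤ ECGs ➤ Physical Examination". The methods cell treats them differently:

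- Hypotension: event rates by treatment, risk difference and relative risk, all with 95% confidence intervals.
- AEs: tabulated by system organ class, preferred term and treatment.
- Vital signs and laboratory tests: "Vital signs and clinical laboratory test results will be listed and summarized by treatment".
- Physical examination: significant findings listed.
- ECGs: "ECG readings will be evaluated by the investigator and abnormalities, if present, will be listed".

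Table 2-2 sets the ECG schedule: "On Day 1, ECG will be collected pre-dose and at hours 2, 4, and 8", and "On Day 8 and Day 14, it will only be collected pre-dose". Section 9.4.3 describes the recording: "Single standard 12-lead ECGs will be recorded after the participant has been resting for at least 5 minutes in the supine position". The investigator then reviews each tracing for clinically significant abnormalities.

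On eligibility, Section 6.2 excludes "arrhythmia with the exception of atrial fibrillation if HR within criteria limit". It also permits pacemakers, ICDs and CRT-D devices, subject to conditions on timing and recent discharges.

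**The concern.** A listing of abnormal readings has no denominator, no planned count by arm and no stated reference to the pre-dose tracing. Some participants will have an abnormal ECG before their first dose, because atrial fibrillation and implanted cardiac devices are allowed. Those participants would be listed whatever treatment they receive, and a reader would have to work out by hand which entries are new and how they divide between the arms.

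The trial has what a simple comparison needs: a concurrent 1:1 placebo arm and a Day 1 pre-dose ECG. At stake is information on new rhythm or conduction findings that the investigator does not consider significant enough to report as an AE. In the visible text these have no by-arm summary.

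**Working it through.** **1. Number of ECGs (Table 2-2).** Day 1: pre-dose, 2, 4 and 8 hours = 4. Day 8: 1. Day 14: 1. Total 4 + 1 + 1 = 6 per participant.

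With about 72 randomised 1:1 (Section 10.1), this is 72 × 6 = 432 tracings, or 36 × 6 = 216 per arm. Table 2-1 adds a screening ECG, giving up to 7 per participant and 72 × 7 = 504 in all. A footnote to Table 2-2 allows one fewer: "If screening and randomization are on the same day all evaluations can be performed only once".

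**2. Routes to a by-arm table.**

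| Finding | Route | By-arm output in visible text |
|---|---|---|
| ECG worsening judged significant | Recorded as an AE (Section 9.2.8; Appendix 3) | Yes, in the AE table by preferred term |
| New ECG abnormality judged not significant | Listing only | None |
| Abnormality already present pre-dose | Listing only | None, and not marked as pre-existing in the stated method |
| Laboratory abnormality judged significant | Recorded as an AE (Section 9.2.6) | Yes, in the AE table and also in the laboratory summary |

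The last row is the useful comparison. Laboratory abnormalities have an AE route of the same kind, yet the plan still summarises laboratory results by treatment.

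**3. Precision of a by-arm comparison.** The documents give no rate of new ECG abnormalities, so equal rates p of 5% to 30% in both arms are assumed. The approximate (Wald) 95% half-width for the risk difference is 1.96 × √(2p(1−p)/n).

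At p = 5% and n = 36: 1.96 × √(2 × 0.05 × 0.95/36) = 0.101, or about 10 points.

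| Assumed rate in both arms | n = 36 per arm (72 randomised) | n = 30 per arm (60 completers) |
|---|---|---|
| 5% | ±10.1 points | ±11.0 points |
| 10% | ±13.9 points | ±15.2 points |
| 20% | ±18.5 points | ±20.2 points |
| 30% | ±21.2 points | ±23.2 points |

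The Wald formula serves here only to show the scale. At 5% the expected count is 0.05 × 36 = 1.8 events per arm, where Wald intervals are unreliable. The reported interval should therefore come from a small-sample method.

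**The case against.** **A reader might infer that the plan has no between-arm comparison of ECG findings.** The documents do not support that. Section 9.2.8 requires significant ECG worsening to be recorded as an AE, Appendix 3 counts clinically significant ECG results as AEs, including those that worsen from baseline, and Section 10.3.2 tabulates AEs by treatment. What remains is that this route depends on the investigator's threshold, spreads ECG findings over preferred terms and gives no shift from baseline.

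**A reader might also infer that a primary endpoint lacks an analysis.** Table 4-1 and the Synopsis name clinically relevant hypotension as the only primary endpoint, and Sections 3.3 and 5.4 are built around hypotension. ECGs are primary only in the row label of Section 10.3.2. Physical examination findings in that row are also only listed, and no section names an ECG signal of concern.

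**The layout of the listing is not described.** It may carry treatment and visit columns, so new findings could perhaps be picked out by hand. That stands. The gap is the missing planned count, not an impossibility.

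**The data may not support everything one would want.** Section 9.4.3 has the investigator assess tracings and keep copies in the source documents. Nothing shows that graded readings or ECG intervals are entered in the CRF, so it cannot be assumed that a full shift table or interval summary needs no new data. This stands, and the fix is conditional on it.

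**Unseen text.** Sections 7.3 and 10.3.5 refer to a statistical analysis plan whose text is not in the supplied material, and parts near Sections 9.4.3 and 10.3.2 are redacted or missing. A by-arm ECG table there cannot be excluded. The ECG sentence in Section 10.3.2 is complete as it stands, however, and specifies a listing.

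**Conclusion.** The point holds for the visible text. Section 10.3.2 gives ECG readings no by-treatment or baseline-referenced summary, although it gives a by-treatment summary to vital signs and laboratory results. Only changes that the investigator judges significant reach a by-arm table, through AEs.

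The size is modest. About 432 scheduled tracings from Day 1 would have no planned by-arm summary of the readings. A comparison would carry a half-width of roughly 10 to 21 points at 36 per arm, or 11 to 23 at 30 per arm, under the assumed equal rates of 5% to 30%. It would be descriptive and could miss a modest excess.

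That some abnormalities will pre-exist follows from the eligibility criteria. How many is unknown, because the documents give no prevalence. The matter is a minor improvement and leaves the hypotension analysis untouched.

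**What to change.** In Section 10.3.2, or in the statistical analysis plan if that is where table specifications sit, keep the listing and add the following:

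1. By treatment, the number and percentage of participants with an ECG abnormality not present on the Day 1 pre-dose ECG, shown for Day 1 post-dose (2, 4 and 8 hours), Day 8 and Day 14. State the denominator as participants with a pre-dose reading and at least one reading in that period.
2. The risk difference with a 95% confidence interval from a small-sample method such as Newcombe, labelled as descriptive.
3. A shift table from the Day 1 pre-dose reading, and interval summaries, only if the CRF captures graded readings or intervals. Check this before committing to either.

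If the statistical analysis plan already contains such a table, a cross-reference in Section 10.3.2 is enough.

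The cost is one or two extra tables. Item 1 needs no added ECGs, but it does need the abnormality findings to be recorded by visit, including pre-dose. The downside is imprecise estimates from single, site-read tracings, which the descriptive label should make plain.

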10.3.3 PK Analyses

Endpoint	Statistical Analysis Methods
Serum PK parameters in participants with HF	PK parameters will be listed, plotted and summarized descriptively

Abbreviations: HF = heart failure; PK = pharmacokinetic.

10.3.5 Interim Analyses

An IA to evaluate clinically relevant hypotension for the purpose of future study planning will be conducted when 1) approximately 30 participants complete the Day 14 End of Study Visit, and 2) approximately 15 of these have baseline SBP less than or equal to 125 mmHg. Details of the analysis conducted at the IA will be described in the statistical analysis plan.

